## **10.4. Fecal Sample Collection**

Fecal sampling for shedding will be performed.

Prior to dosing, a baseline stool sample will be collected, if available, followed by collections during and following the completion of blinded study drug administration. Post dosing samples will be collected until discharge as outlined in the schedule of procedures.

Diapers of infants will be checked at least every 6 hours per standard NICU practice. During the first 4 days of dosing, all fecal samples will be collected. After Day 4, samples will be collected one

time per week. If there are multiple samples per day, only a single sample will be collected for processing.

Fecal samples will be collected, processed and shipped to a central laboratory as described in the study laboratory manual. For samples that cannot be processed and frozen immediately after collection, the sample (diaper) may be stored under refrigerated conditions until freezing. Freezing of samples must occur within 12 hours of collection. The time of collection and freezing of the samples will be recorded.

Fecal samples will be analyzed for [REDACTED] using qPCR.

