6.2.2 Windows

The time schedule described in the protocol for each scheduled activity will be followed as closely as possible. The time windows noted in Table 4 will be used for analysis purposes.

Table 4: Analysis Visit Windows for Dosing Period and Post Dosing

Nominal Visit during dosing period (Target Day)	Protocol Window	Study Day Analysis Visit Window Range
Baseline	Collected at birth, screening, or/and Week 1 Day 1 before study dosing	Sample assessment date < Date of First Dose of study treatment
1 Hour ^a	1 Hour + 10 minutes	1 Hour + 30 minutes

Nominal Visit during dosing period (Target Day)	Protocol Window	Study Day Analysis Visit Window Range
2 Hour ^a	2 Hour \pm 10 minutes	2 Hour \pm 30 minutes
3 Hour ^a	3 Hour \pm 10 minutes	3 Hour \pm 30 minutes
4 Hour ^a	4 Hour \pm 10 minutes	4 Hour \pm 30 minutes
8 Hour ^a	8 Hour \pm 10 minutes	8 Hour \pm 30 minutes
12 Hour ^a	12 Hour \pm 10 minutes	12 Hour \pm 30 minutes
16 Hour ^a	16 Hour \pm 10 minutes	16 Hour \pm 30 minutes
20 Hour ^a	20 Hour \pm 10 minutes	20 Hour \pm 30 minutes
24 Hour ^a	24 Hour \pm 10 minutes	24 Hour \pm 30 minutes
Week 1 (Day 1-4) ^b	day 1, day 2, day 3, day 4	day 1, day 2, day 3, day 4
Week 1 (Day 5-7) ^{b,c,d}	day 5, day 6, day 7	day 5, day 6, day 7
Week 2 (Day 14) ^{b,d}	13 to 16 days	13 to 17 days
Week 3 (Day 21) ^b	20 to 22 days	18 to 24 days
Week 4 (Day 28) ^{b,d}	25 to 32 days	25 to 32 days
Week 5 (Day 35) ^b	34 to 36 days	33 to 38 days
Week 6 (Day 42) ^{b,d}	41 to 42 days	39 to 45 days
Week 7 (Day 49) ^b	48 to 50 days	46 to 52 days
Week 8 (Day 56) ^{b,d}	55 to 57 days	53 to 59 days
Week 9 (Day 63) ^b	62 to 64 days	60 to 66 days
Week 10 (Day 70) ^{b,d}	69 to 71 days	67 to 73 days
Week 11 (Day 77) ^b	76 to 78 days	74 to 80 days
End of Dosing or Hospital Discharge ^{b,d} (for Growth Assessment, and fecal sample only)	Not specified	For fecal sample: sample assessment date - last dose date \geq 0 For growth assessment: 0 \leq sample assessment date - last dose date \leq 5 days
Nominal Visit during Post Dosing		Post Study Day Analysis Visit Window Range^e
Post Dosing 1 Week ^d	5 to 9 days	6day \leq (assessment date – expected last dose date+1) \leq 13 days
Post Dosing 1 Month ^d	30 to 35 days	21 days \leq (assessment date – expected last dose date+1) \leq 35 days
Post Dosing 3 Month ^d	85 to 99 days	85 \leq (assessment date – expected last dose date+1) \leq 99 days

Nominal Visit during dosing period (Target Day)	Protocol Window	Study Day Analysis Visit Window Range

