Post Dosing 6 Month ^d	181 to 195 days	181 <= (assessment date – expected last dose date+1) <= 195 days
Post Dosing 18 Month/End ^d	Not specified	520 <= (assessment date – expected last dose date+1) <= 576 days
Withdrawal Prior to Post Dosing 6 Month ^d	Not specified	assessment date >= date of withdrawal and (assessment date – expected last dose date+1) <= 181 days
Withdrawal between Post Dosing 6 and 18 Month ^d	Not specified	assessment date >= date of withdrawal and 196 days < (assessment date – expected last dose date+1) < 520 days

- a- Windows for vital sign measurements and physical examinations.
- b- Window for fecal sample.
- c- Window for IVH measurement.
- d- Windows for growth assessment (note that Post Dosing 18 Month data will only be presented in listings).
- e- Windows for Post Dosing may be adjusted to account for patients that terminated dosing early. For example, if a subject early terminates dosing at Week 10 but was expected to complete dosing at Week 11, then the Post Dosing window will be adjusted to reflect planned time point after expected dosing completion.

If a subject has more than 1 assessment occurring in the same visit window, the data from the visit closest to the scheduled study day will be used for summaries. If two assessments have the same distance from the scheduled study day, the assessment after the scheduled study day will be used for the analyses.

If multiple assessments occur as Baseline (screening or Day 1 prior to dosing), then the last assessment before the first study dose will be used for the analyses.

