6.4.2 Secondary Efficacy Variables

The secondary efficacy variables are:

- Incidence of suspected NEC (stage I)
- Incidence of confirmed NEC (stage II and higher)
- Incidence of Feeding intolerance
- Death
- Incidence of Sepsis
- Incidence of other neonatal complications of prematurity
 - ROP
 - IVH
 - BDP
 - Spontaneous Gastrointestinal Perforation
 - Patent ductus arteriosus requiring treatment with indomethacin, ibuprofen or surgery
- Number and percent of subject with STP206 organism (STP-6, STP-11) identified
- Time to first detection of STP206 organism (STP-6, STP-11)
- Number and percent of subjects that fall in the four growth classifications 1) appropriate for gestational age (AGA), 2) small for gestational age (SGA/Head-Spared), 3) SGA/Symmetric, and 4) large for gestational age (LGA). Where AGA is defined as both body weight (g) and head circumference (cm) are between 10th Percentile and 90th Percentile according to the gender specific growth Percentile charts. SGA/Head-Spared is defined as Body Weight (g) is <10th percentile, and Head circumference (cm) is between 10th Percentile and 90th Percentile according to the gender specific growth percentile charts. SGA/Head-Symmetric is defined as Both Body Weight (g) and Head circumference (cm) are <10th Percentile according to the gender specific growth percentile charts. LGA is defined as Both Body Weight (g) and Head circumference (cm) are >90th Percentile according to the growth percentile charts.

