8.7.4 Other Observations Related to Safety

Growth assessments during the dosing period and post dosing period will be summarized as AGA, SGA/Head-Spared, SGA/Symmetric, LGA at the following time points: Pre-dose, Week 1 (Days 5-7), Week 2, 4, 6, 8, 10, and Post Dosing 1 Week, Post Dosing 1, 3 6 Month, and Early Withdrawal Prior to post dosing 6 Months. Four classifications (AGA, SGA/Head-Spared, SGA/Symmetric, and LGA) according to the growth chart for males and females will be summarized and displayed. Classifications will be based on weight and head growth measurements¹³ specified in Appendix D of the protocol and the WHO standard growth charts https://www.cdc.gov/growthcharts/who_charts.htm.

Information on feeding method (bottle, breast, and tube) and content of feedings (formula or breast milk), abdominal evaluation, etc will be summarized by number and percent of subjects.

Physical examination will be summarized by the number and percent of subjects with abnormal findings at the following time points: Pre-dose, and 3 hours Post Dosing.

Vital signs (BP, HR, RR, and Temperature) will be summarized as descriptive statistics (N, mean, SD, median, 25th and 75th quartiles, minimum, and maximum) and change from baseline at the following time points: Pre-dose, 1 hour, 2, 3, 4, 8, 12, 16, 20 and 24 hours post dosing.

The number and percentage of subjects with presence of STP206 organisms in fecal samples will be summarized, and the quantity (CFU) of the STP206 organisms detected from fecal shedding will be further summarized as descriptive statistics (N, mean, SD, median, 25th and 75th quartiles, maximum, and minimum) at the following time points: Pre-dose, Week 1 Days 1- 4), Week 1 (Days 5-7), Week 2, 3, 4, 5, 6, 7, 8, 9, 10, 11, End of Dosing or Hospital Discharge, whichever occurs first.

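### The SAP's one-assessment-per-window rule cannot choose among the daily Day 1–4 stools, leaving the early shedding summary to the programmer; the Week 1 growth window also omits Day 8

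*SAP*

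**What the plan says.** **Sampling.** Protocol 10.4: "During the first 4 days of dosing, all fecal samples will be collected". The same section adds: "If there are multiple samples per day, only a single sample will be collected for processing". After Day 4, stool is taken weekly.

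**Window.** SAP Table 4 (6.2.2) has a single row for Week 1, Days 1 to 4. Its analysis window reads "day 1, day 2, day 3, day 4". From Week 2 onward, each weekly row names one target day.

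**Selection rule.** Below Table 4, when a window holds several assessments, "the data from the visit closest to the scheduled study day will be used for summaries". If two are equally distant, "the assessment after the scheduled study day will be used for the analyses". Stool is not exempted.

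**Summary.** SAP 8.7.4: "The number and percentage of subjects with presence of STP206 organisms in fecal samples will be summarized", together with descriptive statistics of quantity. The listed fecal time points begin "Pre-dose, Week 1 Days 1- 4), Week 1 (Days 5-7), Week 2, 3, 4". No any-positive, maximum or mean rule is given for Days 1–4.

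**Subject-level variables.** SAP 6.4.2 lists the number and percent of subjects with an organism identified, and the time to first detection. Neither has a visit window, and the SAP does not say whether the selection rule applies to them.

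**Growth.** Protocol 11.3.2.2 sets a growth assessment at Day 7 (±1 day). The matching Table 4 row covers Days 5, 6 and 7, and the next row starts at Day 13.

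**The concern.** A mean, SD and quartiles of quantity at one time point need one value per infant, and the SAP does not say how to get that value from up to four stools. Two programmers following the text could report different early shedding figures from the same data, and neither would have departed from the plan.

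Fecal shedding of each component is the first-listed secondary objective (Protocol 6.2.2), and the daily sampling is the part of the design that shows how early the organisms appear. Each cohort has about 8 treated and 4 control infants, so a change of status in one infant visibly moves a percentage.

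The growth issue is smaller. A measurement taken on a day the protocol permits falls between two analysis windows.

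**Working it through.** The plan states no figure on this point, so there is none to reproduce. The check applies the SAP rule literally and then asks how much the outcome could matter.

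**1. Results available.** One processed stool per day over Days 1–4 gives up to four results per infant, and fewer if no stool is passed. If the one-per-day sentence in Protocol 10.4 is read as covering only the period after Day 4, there could be more than four.

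**2. Apply the rule.** Distance = |stool day − scheduled day|, for stools on Days 1, 2, 3 and 4.

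| Scheduled day taken as | Distances | Stool kept |
|---|---|---|
| all four days, as the row lists them | 0, 0, 0, 0 | none selected: all tied, none after its scheduled day |
| Day 1 | 0, 1, 2, 3 | Day 1 |
| midpoint 2.5 | 1.5, 0.5, 0.5, 1.5 | Day 3, by the tie-break |
| Day 4 | 3, 2, 1, 0 | Day 4 |

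The literal text selects nothing. Each workable target is an addition to the plan, and each drops up to three of four results from the summary.

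**3. Why the choice could matter (assumed rates).** The documents give no per-stool detection probability. If detection rose as 10%, 30%, 50%, 70% over Days 1–4, the reported figure would be 10%, 50% or 70% for the three targets above.

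**4. Range of any understatement (assumed rates).** Compare one stool with any positive among four, for a constant p = 0.3:

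- Independent stools: 1 − 0.7^4 = 1 − 0.2401 = 76.0%, a gap of 46 points.
- Within-infant correlation ρ = 0.5, beta-binomial. With s = 1/ρ − 1 = 1, P(no positive) is the product over i = 0 to 3 of ((1 − p)s + i)/(s + i). This is 0.7 × 0.85 × 0.9 × 0.925 = 0.495, so 50.5%, a gap of about 20 points.
- Fully concordant stools: 30%, a gap of zero.

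The gap runs from nil to large, and nothing in the documents places it within that range.

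**5. Cohort granularity.** Protocol 7.1 has 12 subjects per group at 2:1, so 8 treated and 4 control. One infant is 1/8 = 12.5 points in a treated arm and 1/4 = 25 points in a control arm.

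**6. The Day 1 stool.** Protocol 11.3.2.1 lists a fecal sample among the Day 1 procedures done before dosing. Table 4 defines baseline by a date earlier than the first-dose date, whereas the text below it counts pre-dose Day 1 assessments as baseline. By date alone, a pre-dose stool on Day 1 falls in the Day 1–4 window and could be summarised as on-treatment.

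**7. Growth and second-week stools.** Day 7 (±1 day) permits Days 6, 7 and 8. Table 4 covers Days 5–7 and resumes at Day 13, so Day 8, one of three permitted days, enters no weekly summary. The scheduled second-week stool is Day 14 (±1 day) in Protocol 11.3.2.3, that is Days 13–15, all inside the 13–17 window.

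**The case against.** The strongest reply is that the comma list in Table 4 means four daily windows. With one processed stool per day, the selection rule would then never be needed. The later rows use ranges, which gives this reading some support. Against it, the four days share one row and one nominal visit, and SAP 8.7.4 names them as one time point with one set of descriptive statistics. The table shells, which SAP section 11 places in a separate document, may settle the matter, but the SAP text does not. What stands is that the intention may have been four time points; the wording still needs correction.

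A reader might go further and infer that early detection is understated by a definite amount. For example, with per-stool rates of 10% to 50% and correlation from 0 to 0.6, the gap from any-positive detection is about 7 to 46 points. The documents do not support this. The rates are assumed, the range leaves out full concordance, and the SAP never names any-positive as its target.

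Nor do the documents show that detection in a cohort, or organisms in controls, would be hidden. The subject-level variables in SAP 6.4.2 carry no visit window, weekly stools follow, and Listing 16.2.8.5.1 covers fecal evaluations.

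A reader might also infer that second-week stools are lost. No scheduled stool falls on Days 8–12, and leaving an unscheduled one out of a visit summary is ordinary windowing.

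It is also true that the outcome is descriptive, that comparisons are exploratory (SAP 7.1), and that the stopping criteria in Protocol 7.1.1 do not use fecal detection.

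**Conclusion.** The point holds as a gap in specification. As written, SAP 6.2.2 and 8.7.4 do not determine the Day 1–4 fecal summary: the result depends on a target day chosen outside the plan and may leave out up to three of four stools. This follows from the text, given one processed stool per day and a single time point. The direction and size of any effect on the reported percentage do not follow from the text. Relative to any-positive detection the shortfall cannot be negative, and it is zero when an infant's stools agree.

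The Day 8 growth omission is a separate mismatch with the protocol, limited to one permitted day.

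No error rate, power or stopping criterion is affected. Both items merit correction before database lock because they concern planned summaries of secondary endpoints and the remedy is wording.

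**What to change.** - **SAP 6.2.2 and 8.7.4, fecal time points.** List Days 1, 2, 3 and 4 as four separate time points, each with its own window. On Day 1, use post-dose stools only and treat a pre-dose Day 1 stool as baseline.
- **SAP 6.4.2 variables.** State that the number and percent with an organism identified, and the time to first detection, use all post-dose stools and are exempt from the one-assessment-per-window rule.
- **Any-positive on Days 1–4.** If wanted, make it supplementary and label it as not comparable with the later single-stool weeks. Otherwise the heavier early sampling alone would make early shedding look higher.
- **Week 1 growth window.** Extend it to include Day 8. Widening Week 2 to take in unscheduled stools from Days 8–12 is optional.

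The cost is a SAP wording change, minor extra programming and longer fecal tables. No sampling beyond what the protocol already requires is needed.

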6.2.3 Dosing Duration

The subject's gestational age at birth will dictate how many weeks of dosing will be administered as outlined in the table below. Subject's gestational age will be reported by the treating physician and/or Principal Investigator on the e-CRF. It is intended that neonates will receive blinded study treatment through 34 weeks post conceptional age. However, in the event of early hospital discharge, the minimum required dosing duration is provided in the table below.

Gestational Age at Birth	Protocol Defined Gestational Age	Intended Dosing Duration Weeks (Days)	Minimum Required Cumulative Dosing Days^{ab}
23 Weeks 0/7 days to 23 Weeks 6/7 days	23 weeks	11 (77)	54
24 weeks0/7 days to 24 Weeks 6/7 days	24 weeks	10 (70)	49
25 weeks0/7 days to 25 Weeks 6/7 days	25 weeks	9 (63)	45
26 weeks0/7 days to 26 Weeks 6/7 days	26 weeks	8 (56)	40
27 weeks0/7 days to 27 Weeks 6/7 days	27 weeks	7 (49)	35
28 weeks0/7 days to 28 Weeks 6/7 days	28 weeks	6 (42)	30
29 weeks0/7 days to 29 Weeks 6/7 days	29 weeks	5 (35)	25
30 weeks0/7 days to 30 Weeks 6/7 days	30 weeks	4 (28)	20
31 weeks0/7 days to 31 Weeks 6/7 days	31 weeks	3 (21)	15
32 weeks0/7 days to 32 Weeks 6/7 days	32 weeks	2 (14)	10

a – over the first 2 weeks of dosing, neonates should receive study drug for a minimum of 5 of the 7 dosing days

b – $\geq 75\%$ of intended number of dosing days

6.3 Baseline Assessments

The following baseline assessments will be conducted prior to initial study treatment administration:

- History and baseline characteristics, including:
 - Maternal history and baseline characteristics
 - Pregnancy history and delivery information
 - Infant history and baseline characteristics
- Physical Examination
- Vital Signs
- Growth Assessment (Head circumference, body length, and body weight)
- Fecal sample, if produced
- Laboratory Assessments

- Peripheral Blood Culture (from NICU admission, if obtained)
- Prior medications

6.4 Efficacy Variables

6.4.1 Primary Efficacy Variable(s)

No primary efficacy variable is defined for this study.

6.4.2 Secondary Efficacy Variables

The secondary efficacy variables are:

- Incidence of suspected NEC (stage I)
- Incidence of confirmed NEC (stage II and higher)
- Incidence of Feeding intolerance
- Death
- Incidence of Sepsis
- Incidence of other neonatal complications of prematurity
 - ROP
 - IVH
 - BDP
 - Spontaneous Gastrointestinal Perforation
 - Patent ductus arteriosus requiring treatment with indomethacin, ibuprofen or surgery
- Number and percent of subject with STP206 organism (STP-6, STP-11) identified
- Time to first detection of STP206 organism (STP-6, STP-11)
- Number and percent of subjects that fall in the four growth classifications 1) appropriate for gestational age (AGA), 2) small for gestational age (SGA/Head-Spared), 3) SGA/Symmetric, and 4) large for gestational age (LGA). Where AGA is defined as both body weight (g) and head circumference (cm) are between 10th Percentile and 90th Percentile according to the gender specific growth Percentile charts. SGA/Head-Spared is defined as Body Weight (g) is <10th percentile, and Head circumference (cm) is between 10th Percentile and 90th Percentile according to the gender specific growth percentile charts. SGA/Head-Symmetric is defined as Both Body Weight (g) and Head circumference (cm) are <10th Percentile according to the gender specific growth percentile charts. LGA is defined as Both Body Weight (g) and Head circumference (cm) are >90th Percentile according to the growth percentile charts.

6.4.3 Exploratory Efficacy Variables

Additional efficacy variables are:

- The incidence of suspected NEC (Stage I NEC) in STP206-treated subjects compared to control subjects through hospital discharge
- The incidence of antibiotic usage in STP206-treated subjects compared to control subjects through hospital discharge

6.5 Drug Concentration Measurements and Pharmacokinetic Parameters

Not applicable to this study.

6.5.1 Handling of Outliers

There is no apriori plan to handle outliers for this study, except for observations deemed to be “extreme” outliers. These types of outliers may be excluded from summary analyses but will be included in listings. When an outlier is excluded from a summary table, a footnote will indicate the subject, value, and reason it was excluded.

6.6 Safety Assessments

The following are the safety assessments:

- The incidence and severity of adverse events, serious adverse events, and changes in clinical parameters from baseline through six months after the last dose of blinded study treatment.
- Physical examination through six months after the last dose of the study treatment.
- Vital signs evaluation through six months after the last dose of the study treatment.
- Concomitant medications evaluations for infant through six months after the last dose of the study treatment.
- The assessment of the progression of standard neonatal growth parameters (head circumference, body length, and body weight) in STP206-treated subjects compared to control subjects through 60f corrected age.
- Number and percent of subjects with presence of STP206 organisms in fecal shedding in STP206-treated subjects compared to control subjects through the last dose of blinded study treatment

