### **6.3. Endpoints**

#### **6.3.1. Primary Endpoints**

The incidence and severity of AEs, SAEs and changes in clinical parameters in STP206-treated subjects compared to control subjects from baseline through 30 days after the last dose of blinded study treatment.

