#### **6.3.2. Secondary Endpoints**

The secondary endpoints of the study are:

- The incidence and the severity of AEs and SAEs in STP206-treated subjects compared to control subjects from baseline through six months after the last dose of blinded study treatment
- The incidence of clinical events (NEC, sepsis/bacteremia, feeding intolerance, death, morbidity/complications of prematurity) in STP206-treated subjects compared to control subjects from baseline through hospital discharge
- The assessment of the fecal shedding of STP206 organisms in STP206-treated subjects compared to its baseline and to control subjects through the last dose of blinded study treatment

- The assessment of the changes in routine clinical parameters in STP206-treated subjects compared to control subjects at baseline through the last dose of blinded study treatment
- The assessment of the progression of standard neonatal growth parameters in STP206-treated subjects compared to control subjects through the 6-month postdosing visit.

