### 7.1.2. Study Periods

Subject participation will be classified into four study periods:

- Screening Period – from the time of informed consent through administration of the first dose of study drug.
- Treatment Period – this will be the period when subjects are actively being administered blinded study treatment.
- Immediate Follow-up Period – this period will begin the day following the last dose of blinded study treatment through 30 days following administration of the last dose.
- Long-Term Follow-up Period – this period will begin after completion of the immediate follow-up period.

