#### *13.2.3.2. Safety Data Analysis*

AEs will be assessed from the time the subject receives the initial dose of study drug through 6 months following the last dose. AEs will be coded according to Medical Dictionary for Regulatory Activities (MedDRA) and summarized in frequency tables displaying counts and percentages by body system, preferred term, and treatment group. Subjects reporting multiple events will only be counted once.

In addition, AEs will be summarized by relationship to study drug and by severity. For assessing relationship to study drug, any event with a study drug relationship marked as “possible”, “probable” or “definite/related” on the CRF will be considered related to study drug.

All SAEs will also be summarized in a frequency table.

Medical history (maternal, pregnancy and infant), concomitant medications, and physical examination findings, will also be summarized by treatment group at each timepoint where data was collected.

Information on method (bottle, breast, tube) and content of feedings (formula or breast milk) will be summarized.

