8 STATISTICAL ANALYSIS

All statistical analyses will be performed using SAS® (version 9.4 or higher).

Unless otherwise noted, summary tables will only include data up to the Month 6 Post-Dose visit. Data collected after that will only be included in listings.

Safety and efficacy data will be summarized using BW strata. If deemed necessary, additional analyses may be conducted on pooled data across cohorts, where incidence of clinical events

(NEC, sepsis, feeding intolerance, death, morbidity/complications of prematurity) may be presented.

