8.7.2 Adverse Events

All AE summaries will be presented by the safety population.

All AE tables will include only treatment emergent AEs (TEAEs) unless otherwise noted. TEAEs are those which start or worsen in severity after the first dose of study medication. If it

cannot be determined if the AE started or worsened after the first dose of study treatment, it will be assumed to be a TEAE.

AEs will be assessed from the time the subject receives their initial dose of study medication up to 6 months following the last dose of study drug (note that some sites used 6 months gestational age rather than 6 months post last dose). All AEs reported during this period, regardless of severity relationship to blinded study treatment, will be recorded. The investigator's verbatim term of each adverse event will be mapped to the system organ class and preferred term using the MedDRA dictionary.

All AE tables will be summarized for each treatment group by system organ class (SOC) and preferred term (PT) using counts and percentages.

In order to count the number of subjects who experienced each AE, a subject experiencing the same AE multiple times will only be counted once for the corresponding preferred term. Similarly, if a subject experienced multiple AEs within the same SOC, that subject will be counted only once for that SOC. Adverse events will be presented in alphabetical order of SOC and within each SOC, in decreasing order of the total number of subjects who experienced each AE at the preferred term level.

Adverse events will also be presented by severity for Mild AE (Grade 1), Moderate AE (Grade 2) and Severe AE (Grade 3). In the case of multiple experiences with the same AE, the subject will be counted only once under the worst reported severity. Missing category will be presented to summarize any missing severity.

Serious adverse events (SAEs) will be presented by SOC and preferred term.

Adverse events will also be summarized by relationship. Treatment related AEs include those events that were rated by the investigator as possible or probable related. Missing category will be presented to summarize any missing relationship.

The following AE categories will be summarized:

- Overall AE summary
- AEs by SOC and preferred term
- Related AEs by SOC and preferred term
- Grade 3 AEs by SOC, preferred term and relationship to study treatment
- Treatment Related AEs with Grade 3 by SOC, preferred term

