14.3.1.4.1	Grade 3 TEAEs by System Organ Class and Preferred Term by Birth Weight Stratification (2000 - 1501 g, 1500 – 1000 g)\Safety Population
14.3.1.4.2	Grade 3 TEAEs by System Organ Class and Preferred Term by Birth Weight Stratification (999 - 750 g, 749 – 500 g)\Safety Population
14.3.1.4.3	Grade 3 TEAEs by System Organ Class and Preferred Term Across All Birth Weight Stratifications\Safety Population
14.3.1.5.1	Treatment Related TEAEs by System Organ Class and Preferred Term by Birth Weight Stratification (2000 - 1501 g, 1500 – 1000 g)\Safety Population
14.3.1.5.2	Treatment Related TEAEs by System Organ Class and Preferred Term by Birth Weight Stratification (999 - 750 g, 749 – 500 g)\Safety Population
14.3.1.5.3	Treatment Related TEAEs by System Organ Class and Preferred Term Across All Birth Weight Stratifications\Safety Population
14.3.1.6.1	Grade 3 Treatment Related TEAEs by System Organ Class and Preferred Term by Birth Weight Stratification (2000 - 1501 g, 1500 – 1000 g)\Safety Population

14.3.1.6.2	Grade 3 Treatment Related TEAEs by System Organ Class and Preferred Term by Birth Weight Stratification (999 - 750 g, 749 – 500 g)\Safety Population
14.3.1.6.3	Grade 3 Treatment Related TEAEs by System Organ Class and Preferred Term Across All Birth Weight Stratifications\Safety Population
14.3.2.1.1	Treatment Emergent SAEs by System Organ Class and Preferred Term and Birth Weight Stratification (2000 - 1501 g, 1500 – 1000 g)\Safety Population
14.3.2.1.2	Treatment Emergent SAEs by System Organ Class and Preferred Term by Birth Weight Stratification (999 - 750 g, 749 – 500 g)\Safety Population
14.3.2.1.3	Treatment Emergent SAEs by System Organ Class and Preferred Term Across All Birth Weight Stratifications\Safety Population
14.3.2.2.1	TEAEs Leading to Discontinuation of Study Treatment by System Organ Class and Preferred Term and Birth Weight Stratification (2000 - 1501 g, 1500 – 1000 g)\Safety Population
14.3.2.2.2	TEAEs Leading to Discontinuation of Study Treatment by System Organ Class and Preferred Term and Birth Weight Stratification (999 - 750 g, 749 – 500 g)\Safety Population
14.3.2.2.3	TEAEs Leading to Discontinuation of Study Treatment by System Organ Class and Preferred Term Across All Birth Weight Stratifications\Safety Population
14.3.2.3.1	TEAEs Leading to Death by System Organ Class and Preferred Term and Birth Weight Stratification (2000 - 1501 g, 1500 – 1000 g)\Safety Population

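### The primary safety endpoint runs to 30 days after the last dose, but the SAP plans AE and SAE summaries only through six months

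*SAP*

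**What the plan says.** Protocol 6.3.1 sets the primary endpoint as the incidence and severity of AEs and SAEs, and changes in clinical parameters, in treated infants "compared to control subjects from baseline through 30 days after the last dose of blinded study treatment". The synopsis says the same. Protocol 6.3.2 lists AEs and SAEs again as a secondary endpoint, this time "compared to control subjects from baseline through six months after the last dose of blinded study treatment". The 30-day limit is also a named study period: for Immediate Follow-up, "this period will begin the day following the last dose of blinded study treatment through 30 days following administration of the last dose" (protocol 7.1.2).

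The protocol's own safety analysis section does not carry the 30-day window forward. In 13.2.3.2, "AEs will be assessed from the time the subject receives the initial dose of study drug through 6 months following the last dose".

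The SAP follows that section. SAP 6.6 lists the incidence and severity of AEs and SAEs and "changes in clinical parameters from baseline through six months after the last dose of blinded study treatment". SAP 8 states that, unless otherwise noted, "summary tables will only include data up to the Month 6 Post-Dose visit". SAP 8.7.2 collects AEs "up to 6 months following the last dose of study drug" and limits the tables to treatment-emergent events, defined by a start or worsening after first dose, with no upper limit at 30 days. Table titles in section 11, for example "Treatment Emergent SAEs by System Organ Class and Preferred Term and Birth Weight Stratification", name no period. SAP 5.2 declares one change from the protocol's analyses, the ITT definition.

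**The concern.** Safety and tolerability are the trial's primary objective. In a descriptive study the prespecified summary is itself the primary result. If the SAP is followed as written, the report will contain AE and SAE counts for the secondary window and none for the primary one. Someone would then have to define the 30-day cut after the SAP is final, possibly after unblinding, with choices still open about which last-dose date to count from and which summaries to show.

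**Working it through.** No power, alpha or sample-size figure is involved. The check is a count of planned tables, a search for any 30-day cut, and a comparison of window lengths.

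**1. Planned AE/SAE tables (SAP section 11).** There are nine families, each in three layouts (the two heavier strata, the two lighter strata, all strata):

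- overall TEAEs (14.3.1.2.1–3)
- overall TEAEs by gestational age (14.3.1.2.5–7)
- TEAEs by SOC/PT (14.3.1.3.1–3)
- Grade 3 (14.3.1.4.1–3)
- treatment-related (14.3.1.5.1–3)
- Grade 3 treatment-related (14.3.1.6.1–3)
- SAEs (14.3.2.1.1–3)
- leading to discontinuation (14.3.2.2.1–3)
- leading to death (14.3.2.3.1–3)

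9 × 3 = 27 tables. Tables given a 30-day cut by title or by SAP text: 0. The titles state no window at all, so the evidence for six months is the text of SAP 6.6, 8 and 8.7.2.

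**2. Other places where 30 days or one month appears in the SAP.** Section 7.4.2 gives the DSMC 30-day post-dosing data. Table 4 has a one-month visit window, but it is footnoted for growth assessment and counts from the expected last dose. Neither is an AE/SAE summary.

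**3. Can the 30-day result be read from the six-month tables?** No. Under SAP 8.7.2 an infant counts once per preferred term and once at worst severity. An infant with a mild event in week 1 and a severe recurrence of the same term in month 5 appears only as severe.

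**4. How different are the windows?** Intended dosing is 14 to 77 days (protocol Table 2), and the six-month visit falls 181 to 195 days after dosing. Taking intended durations:

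- Shortest dosing: primary window 14 + 30 = 44 days. Table window 14 + 181 = 195 to 14 + 195 = 209 days. Share 44/209 = 0.211 to 44/195 = 0.226.
- Longest dosing: primary window 77 + 30 = 107 days. Table window 77 + 181 = 258 to 77 + 195 = 272 days. Share 107/272 = 0.393 to 107/258 = 0.415.

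The primary window is about 21% to 41.5% of the time the tables cover. This is a share of time, not of events; the documents give no event timing, so the effect on counts cannot be estimated.

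**5. Size of the repair.** Three summaries (TEAEs by SOC/PT, TEAEs by worst severity, SAEs by SOC/PT) × 3 layouts = 9 tables if done separately. The three worst-severity tables have no titled counterpart in section 11, which lists only Grade 3.

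**The case against.** The strongest reply is that little is at stake. Comparisons are exploratory, the sample size has no statistical basis, and every 30-day event is inside the six-month tables. The SAP also plans listings of all AEs and SAEs, and onset date and time are recorded (protocol 10.3.5 and 12.3). With about 100 to 110 infants, a 30-day subset could be rebuilt if the listings show onset. All of that stands, and it limits the consequence. It does not supply the missing summary, because listings are not a tabulation of incidence and severity by dose group and stratum.

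Four further defences carry less weight.

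- The DSMC sees 30-day data, but this is cohort-by-cohort monitoring. As scheduled it also does not name 30-day data for group 4a: the reviews of 1b to 4a bring in 1a to 3b, and the last names 4b.
- Section 11 allows tables to be added, and the shells are in a separate document not available here. A 30-day cut could exist there, but neither document plans one.
- The six-month sentence in SAP 6.6 is correct for the collection period and the secondary endpoint. The defect is an omission beside it.
- The SAP follows protocol 13.2.3.2. True, which means the gap begins in the protocol.

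A reader might infer that the sponsor replaced the primary endpoint with the six-month one. The documents do not support that: SAP 5.2 declares no such change, and the SAP never restates the primary endpoint in any form. A reader might also infer that the clinical-parameter half of the endpoint goes unanalysed after Day 1. That cannot be settled here. SAP 6.6 gives vital signs and physical examination a six-month scope, while 8.7.4 summarises them only to 24 hours and 3 hours after dosing. Later NICU values stay off the CRF, with adverse findings recorded as AEs or, for examinations, as AEs or complications of prematurity (protocol 10.3.1, 10.3.2). Whether values from the post-dosing visits are on the CRF is not stated.

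**Conclusion.** The point holds for AEs and SAEs. The primary endpoint has a 30-day window fixed in the protocol, and 0 of 27 planned AE/SAE tables is assigned to it. What is missing is a planned summary; the data and the definition of the window both exist. No test, error rate or power is affected. The six-month tables are a poor stand-in: they cover roughly two and a half to five times as long (258/107 = 2.4; 209/44 = 4.75), and SAP 8.7.2 itself notes that some sites counted six months from a different origin.

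This rests on two assumptions: that the unseen table shells contain no 30-day cut, and that intended dosing durations represent actual ones for the window comparison. The mismatch for vital signs and physical examination is a separate and lesser matter whose extent depends on the CRF.

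**What to change.** In SAP 6.6, 8.7.2 and section 11, add Safety-population summaries of TEAEs (by SOC/PT and by worst severity) and of SAEs, with onset from first dose through actual last dose plus 30 days. Show them by dose group and stratum and across all strata. Separate tables or a period column in existing tables would both serve. Label these primary and the six-month tables secondary. Specify the actual last dose, because the SAP's post-dosing visit windows count from the expected one. Align protocol 13.2.3.2 with 6.3.1, or record the difference in SAP 5.2.

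Do not send the 30-day summary to the per-protocol population through SAP 8.3.3, which promises to repeat an undefined primary analysis there. That population excludes infants below the minimum dosing days unless they have confirmed NEC, so it would drop most who stopped early, including those who stopped for an AE. It would also conflict with SAP 8.7. State that safety summaries use the Safety population and reconcile the 8.3.3 sentence with that. Section 11 gives no guidance on it: its six per-protocol tables are all infant baseline characteristics.

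Separately, reconcile SAP 6.6 with 8.7.4 for vital signs and physical examination. If the CRF holds post-dosing visit values, summarise them and add the visit windows that Table 4 lacks for these measures. If it does not, say that findings after Day 1 enter only through recorded AEs or complications of prematurity.

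The cost is SAP wording, one filter on recorded onset dates, and about nine tables or the equivalent columns, of which three need a new layout. No new data collection is needed for the AE/SAE part.
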